C_{max}	maximum observed concentration of drug
C_{tau}	observed drug concentration at the end of the dosing interval
$t_{1/2}$	estimate of the terminal elimination half-life of the drug, calculated by dividing the natural log of 2 by the terminal elimination rate constant (λ_z)
T_{last}	time (observed time point) of C_{last}
T_{max}	time (observed time point) of C_{max}
λ_z	terminal elimination rate constant, estimated by linear regression of the terminal elimination phase of the concentration of drug versus time curve

1. INTRODUCTION

This statistical analysis plan (SAP) describes the statistical analysis methods and data presentations to be used in tables, figures, and listings (TFLs) in the clinical study report (CSR) for Cohort 3 from Study GS-US-334-0154. A separate SAP for Cohorts 1 and 2 was finalized on 05 February 2016, and the CSR for Cohorts 1 and 2 was approved on 26 May 2016. The current SAP is based on the study protocol Amendment 4 dated 23 April 2015 and the electronic case report form (eCRF), and will only present the plan for statistical analyses of Cohort 3 of this study. The SAP will be finalized before SVR12 analysis database finalization. Any changes made after the finalization of the SAP will be documented in the CSR.

1.1. Study Objectives

The primary objective of cohort 3 in this study are as follows:

- To evaluate the safety of LDV/SOF for 12 weeks as assessed by review of the accumulated safety data
- To evaluate the efficacy of LDV/SOF for 12 weeks measured by the proportion of subjects with renal insufficiency who have achieved a sustained viral response 12 weeks after treatment discontinuation (SVR12)
- To evaluate the steady state pharmacokinetics of SOF and its metabolites and LDV upon dosing LDV/SOF in subjects with renal insufficiency

The secondary objectives of cohort 3 in this study are as follows:

- To evaluate the proportion of subjects with renal insufficiency who attain SVR at 4 and 24 weeks after discontinuation of treatment (SVR4 and SVR24)
- To evaluate the kinetics of plasma HCV RNA during and after treatment discontinuation
- To evaluate the emergence of viral resistance to SOF and LDV during and after treatment discontinuation

The exploratory objective of cohort 3 in this study is:

PPD

1.2. Study Design

This is a multicenter, open-label study cohort that will evaluate the safety, tolerability, and antiviral efficacy of LDV/ SOF in subjects with chronic renal insufficiency and genotype 1 or 4 HCV infection, including subjects with compensated cirrhosis.

Approximately 35 subjects with severe renal insufficiency will be enrolled as below.

- Cohort 1: 10 subjects will receive SOF 200 mg + RBV 200 mg once daily for 24 weeks.
- Cohort 2: Following review of safety, efficacy and pharmacokinetic (PK) data through post-treatment Week 4 of Cohort 1, 10 additional subjects will receive SOF 400mg + RBV 200mg once daily for 24 weeks.
- Cohort 3: Following review of safety and available PK data through Week 12 of Cohort 2, 15 additional subjects will receive LDV/SOF once daily for 12 weeks.

The total time to complete all study visits in Cohort 3 is approximately 42 weeks including the following periods:

- Up to 42-day (6-week) screening period
- 12-week treatment period
- Up to 24-week posttreatment period

The schedule of assessments is provided as an appendix to the SAP ([Appendix 1](#)).

1.3. Sample Size and Power

Due to the exploratory nature of this study, no formal power or sample size calculations were performed to determine treatment group size. The total sample size of 35 is largely based on feasibility.

2. TYPE OF PLANNED ANALYSIS

2.1. Interim Analyses

2.1.1. SVR12 Analysis

The analysis for the primary endpoint SVR12 will occur after all subjects complete the posttreatment Week 12 visit or prematurely discontinue from the study. All safety and efficacy data through the posttreatment Week 12 visit will be cleaned, finalized and included in the analysis.

2.2. Final Analysis

After all subjects have completed the study or early terminated the study, outstanding data queries have been resolved or adjudicated as unresolvable, and the data have been cleaned and finalized, the final analysis of the data will be performed.

3. GENERAL CONSIDERATIONS FOR DATA ANALYSES

Analysis results will be presented using descriptive statistics. For categorical variables, the number and percentage of subjects in each category will be presented; for continuous variables, the number of subjects (n), mean, standard deviation (SD) or standard error (SE), median, first quartile (Q1), third quartile (Q3), minimum, and maximum will be presented.

By-subject listings will be presented for all subjects in the All Enrolled Analysis Set and sorted by subject ID number, visit date, and time (if applicable). Data collected on log forms, such as AEs, will be presented in chronological order within the subject. Age, sex at birth, race, and ethnicity will be included in the listings, as space permits.

3.1. Analysis Sets

Analysis sets define the subjects to be included in an analysis. Analysis sets and their definitions are provided in this section. The analysis set will be identified and included as a subtitle of each table, figure, and listing.

For each analysis set, the number and percentage of subjects eligible for inclusion, as well as the number and percentage of subjects who were excluded (if any), will be summarized.

3.1.1. All Enrolled Analysis Set

All Enrolled Analysis Set includes all subjects who received a study subject identification number in the study after screening.

3.1.2. Full Analysis Set

The Full Analysis Set (FAS) includes all subjects who were enrolled and took at least 1 dose of study drug. The study drug for Cohort 3 in this study is LDV/SOF. This is the primary analysis set for efficacy analyses.

3.1.3. Safety Analysis Set

The Safety Analysis Set includes all subjects who took at least 1 dose of study drug. This is the primary analysis set for safety analyses.

3.1.4. Pharmacokinetic Analysis Set

The Pharmacokinetic (PK) Analysis Set will include all enrolled subjects who took at least 1 dose of study drug and have at least 1 nonmissing postdose concentration value reported by the PK laboratory. This is the primary analysis set for all PK analyses.

3.2. Subject Grouping

In Cohort 3 of this study, there is only 1 treatment, which is LDV/SOF once daily for 12 weeks. Therefore, for all analysis sets, there will be only 1 group.

3.3. Strata and Covariates

This study does not use a stratified randomization schedule when enrolling subjects. No covariates will be included in efficacy and safety analyses.

3.4. Examination of Subject Subgroups

There are no prespecified subject subgroupings for efficacy analyses.

3.5. Multiple Comparisons

Adjustments for multiplicity will not be made, because no formal statistical testing will be performed in this study.

3.6. Missing Data and Outliers

3.6.1. Missing Data

In general, missing data will not be imputed unless methods for handling missing data are specified. Exceptions are presented in this document.

For missing last dosing date of study drug, imputation rules are described in Section 4.2.1. The handling of missing or incomplete dates for AE onset is described in Section 7.1.5.2, and for prior and concomitant medications in Section 7.3.

For analyses of categorical HCV RNA data, missing posttreatment HCV RNA data will have the missing data imputed. Missing on-treatment HCV RNA will have the missing data imputed up to the time of the last dose (for on-treatment displays). If the study day associated with the last dosing date is greater than or equal to the lower bound of a visit window, and the value at the visit is missing, the value will be imputed. If the study day associated with the last dosing date is less than the lower bound of a visit window then the on-treatment value at that visit will remain missing.

If an HCV RNA data point is missing and is preceded and followed in time by values that are “< lower limit of quantification (LLOQ) target not detected (TND)”, then the missing data point will be set to “< LLOQ TND”. If a data point is missing and preceded and followed by values that are “< LLOQ detected”, or preceded by “< LLOQ detected” and followed by “< LLOQ TND”, or preceded by “< LLOQ TND” and followed by “< LLOQ detected”, then the missing value will be set to “< LLOQ detected”. In these situations the data point will be termed a bracketed success; otherwise, the data point will be termed a bracketed failure (ie, \geq LLOQ detected). If a data point is missing and is not bracketed, the missing data point will also be termed a failure (ie, \geq LLOQ detected) except for SVR24, which will be imputed according to SVR12 status. Success for SVR12 for subjects who have no further HCV RNA measurements collected will be counted as a success for SVR24 due to the high correlation between these 2 endpoints.

For the analyses of continuous HCV RNA efficacy data, when and only when a missing HCV RNA value is imputed as < LLOQ TND or < LLOQ detected according to the imputation rule described above, the corresponding continuous value will be imputed to LLOQ – 1 IU/mL. No other imputation will be performed for continuous HCV RNA data.

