In the efficacy analysis, no statistical hypothesis testing will be performed and no formal inferences will be made on the primary efficacy endpoint SVR12. A point-estimate with two-sided 95% exact confidence interval (CI) using the binomial distribution (Clopper-Pearson method) will be constructed for the SVR12 rate by treatment cohort. Similar analysis will be also performed for secondary endpoints SVR4 and SVR24.

To evaluate the kinetics of circulating HCV RNA during and after treatment discontinuation, viral load data will be listed by subject and summarized by treatment cohort and visit using descriptive statistics.

Due to the exploratory nature of this study, no formal power or sample size calculations were performed to determine treatment group size. The total sample size of 35 is largely based on feasibility.

This study will be conducted in accordance with the guidelines of Good Clinical Practices (GCPs) including archiving of essential documents.

GLOSSARY OF ABBREVIATIONS AND DEFINITION OF TERMS

°C	degrees Celsius
°F	degrees Fahrenheit
β-hCG	β-human chorionic gonadotropin
AE	adverse event
ALT	alanine aminotransferase (also SGPT)
ANC	absolute neutrophil count
APTT	activated partial thromboplastin time
AST	aspartate aminotransferase (also SGOT)
AUC	area under the curve
AUC _{tau}	area under the plasma concentration versus time curve over the dosing interval (tau)
BID	twice a day
BLQ	below the lower limit of quantification
BMI	body mass index
BW	body weight
CL _{cr}	Creatinine clearance
C _{max}	the maximum observed serum/plasma/peripheral blood mononuclear (PBMC) concentration of drug
C _{tau}	observed drug concentration at the end of the dosing interval (tau)
CRF	case report form(s)
CRO	Contract (or clinical) research organization
DAA	direct-acting antiviral
dL	Deciliter
DNA	deoxyribonucleic acid
DSPH	Drug Safety and Public Health
ECG	Electrocardiogram
eCRF	Electronic case report form(s)
ESAs	Erythropoiesis stimulating agents
ESRD	End Stage Renal Disease
EU	European Union
FAS	full analysis set
FDA	(United States) Food and Drug Administration
FEV ₁	forced expiratory volume in one second
GCP	Good Clinical Practice (Guidelines)
GGT	gamma glutamyl transferase
GSI	Gilead Sciences, Inc.
GT	Genotype (viral)
Hb	Hemoglobin
HbA _{1c}	Hemoglobin A _{1c}

GLOSSARY OF ABBREVIATIONS AND DEFINITION OF TERMS (CONTINUED)

HBV	Hepatitis B virus
HCV	Hepatitis C virus
HDPE	high-density polyethylene
HIV	Human Immunodeficiency Virus
HLGT	High-Level Group Term

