8.2.2. Data Handling Conventions

Missing data can have an impact upon the interpretation of the trial data. In general, values for missing data will not be imputed.

For the analysis of post-baseline categorical efficacy endpoints, if a data point is missing and is immediately preceded and followed in time by values that are deemed successes, then the missing data point will be termed a success; otherwise the data point will be termed a failure.

Any subject with missing data due to premature discontinuation of the study medication will be considered a failure at the time points on, or following, the date of discontinuation. If no HCV RNA values are obtained after the last dose of study medication, the subject will be considered a treatment failure for the SVR endpoints.

Where appropriate, safety data for subjects that did not complete the study will be included in summary statistics. For example,

- If a subject received study medication, the subject will be included in a summary of adverse events according to the treatment received; otherwise, if the subject is not dosed then they will be excluded from the summary.
- If safety laboratory results for a subject are missing for any reason at a time point, the subject will be excluded from the calculation of summary statistics for that time point. If the subject is missing a predose value, then the subject will be excluded from the calculation of summary statistics for the predose value and the change from predose values.

Values for missing safety laboratory data will not be imputed; however, a missing baseline result will be replaced with a screening result, if available. If no pretreatment laboratory value is available, the baseline value will be assumed to be normal (i.e., no grade [Grade 0]) for the summary of graded laboratory abnormalities.

Values for missing vital signs data will not be imputed; however, a missing baseline result will be replaced with a screening result, if available.

HCV RNA values below the LLOQ for the assay will be set to the lower limit minus 1 for calculation of summary statistics for the actual HCV RNA values and the change from baseline values by study visit. The reported values will be provided in the HCV RNA listing.

For selected analyses of early time point data, HCV RNA data (IU/mL) may be transformed to the logarithmic (base 10) scale (\log_{10} IU/mL).

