8.4.2. Secondary Analysis

The proportion of subjects with HCV RNA below the LLOQ over time (including SVR12) will be presented by treatment cohort in tabular and graphical form.

Descriptive summaries and listings will be provided for additional efficacy evaluations including the proportion of subjects who experience virologic failure, ALT normalization, serum HCV RNA actual values and change from baseline.

PPD

Details on efficacy analyses will be described in the statistical analysis plan (SAP).

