3.8.2. Analysis Visit Windows

Subject visits might not occur on protocol-specified days. Therefore, for the purpose of analysis, observations will be assigned to analysis windows. Analysis windows are defined for HCV RNA, vital signs, safety laboratory, and electrocardiogram (ECG).

In general, the baseline value will be the last nonmissing value on or prior to the first dose date of study drug.

HCV RNA, vital signs, safety laboratory and ECG data collected up to the last dose date + 2 days are considered to be on-treatment data and HCV RNA, vital signs, safety laboratory and ECG data collected after the last dose date + 2 days are considered posttreatment data.

The analysis windows for on-treatment HCV RNA, vital signs, and safety laboratory data are provided in [Table 3-1](#). The analysis windows for on-treatment ECG data are provided in [Table 3-2](#).

Table 3-1. Analysis Windows for On-treatment HCV RNA, Vital Signs and Safety Laboratory Data

Nominal Visit	Nominal Day	Lower Limit	Upper Limit
Baseline	1	(none)	1
Week 1	7	2	11
Week 2	14	12	21
Week 4	28	22	35
Week 6	42	36	49
Week 8	56	50	63
Week 10	70	64	77
Week 12	84	78	≥ 85

Table 3-2. Analysis Windows for On-treatment ECG Data

Nominal Visit	Nominal Day	Lower Limit	Upper Limit
Baseline	1	(none)	1
Week 4	28	2	42
Week 8	56	43	70
Week 12	84	71	≥ 85

HCV RNA, vital signs, safety laboratory and ECG data collected after the last dose date + 2 days will be assigned to the posttreatment follow-up (FU) visits. Visit windows will be calculated from the last dose date (ie, FU Day = collection date minus the last dose date) as shown in [Table 3-3](#).

Table 3-3. Analysis Windows for Posttreatment HCV RNA, Vital Signs, Safety Laboratory and ECG Data

Nominal FU ^a Visit	HCV RNA			Vital Signs, Safety Laboratory and ECG Data ^b		
	Nominal FU Day	Lower Limit	Upper Limit	Nominal FU Day	Lower Limit	Upper Limit
FU-4	28	21	69	28	3	30
FU-12	84	70	146		NA	
FU-24	168	147	190		NA	

^a FU-x visit = posttreatment Week-x follow-up visit.

^b Vital signs and safety laboratory data will be summarized only for the FU-4 visit (up to 30 days after last dose).

3.8.3. Selection of Data in the Event of Multiple Records in an Analysis Visit Window

Depending on the statistical analysis method, single values may be required for each analysis window. For example, change from baseline by visit usually requires a single value, whereas a time-to-event analysis would not require 1 value per analysis window.

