6.2.2. Analysis Methods for Secondary Efficacy Endpoints

For analyses of HCV RNA < LLOQ (ie, < 15 IU/mL) by visit while on treatment and during the posttreatment (SVR) follow-up period, subjects will be assigned a value at each visit based on the categorical imputation rules described in Section 3.6.1. The 2-sided 95% exact confidence interval based on Clopper-Pearson method will be provided for the proportion. The overall category for “HCV RNA < LLOQ” will be split into the following 2 subcategories: “< LLOQ TND” for subjects with target not detected and “< LLOQ detected” for subjects with < LLOQ in tabular displays.

Graphs for the proportion of subjects with HCV RNA < LLOQ over time during treatment will be displayed.

Summary statistics will be presented for absolute values and change from baseline in HCV RNA (\log_{10} IU/mL) by visit through end of treatment (EOT). Imputation rules described in Section 3.6.1 will be used to assign HCV RNA values for missing values at a visit that are bracketed by “< LLOQ TND” and/or “< LLOQ detected”. Otherwise, a missing = excluded analysis will be performed.

For the SVR12 endpoint analysis, a summary table of the number and percentage of subjects with SVR12, virologic failure (VF), and Other will be created. All subjects who achieve SVR12 will be categorized as SVR12. Virologic failure will be descriptively summarized as “on-treatment virologic failure” and relapse (which will be broken down by study drug completed yes/no). Subjects who do not achieve SVR12 and do not meet criteria for VF will be categorized as Other. The denominator for relapse will be the number of subjects who had HCV RNA < LLOQ on their last observed on-treatment HCV RNA measurement; otherwise, the denominator will be the number of subjects in the FAS.

A concordance table between SVR12 and SVR24 will be provided. Subjects with both observed SVR12 and observed SVR24 data will be included for this analysis.

In addition, the proportion of subjects with ALT normalization (defined as ALT > ULN at baseline and ALT \leq ULN at each visit) will be presented by study visit. Tables for ALT normalization by visit will use methodology similar to the analyses of HCV RNA < LLOQ, but will use a missing = excluded analysis. Only those subjects with ALT > ULN at baseline (defined as the last ALT value collected prior to first dose of study drug) will be included in the analysis of ALT normalization.

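### SAP 3.6.1 counts a Week 12 responder with no later sample as an SVR24 success where Protocol 8.2.2 counts a failure; the departure is not stated and its effect is not tabulated

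*SAP*

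**What the plan says.** SVR24 is a secondary efficacy endpoint (Protocol 8.1.3). After describing the SVR12 estimate with its exact Clopper-Pearson interval by cohort, the protocol synopsis adds: "Similar analysis will be also performed for secondary endpoints SVR4 and SVR24".

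Protocol 8.2.2 sets the rule for missing categorical efficacy values. If the values immediately before and after are both successes, "then the missing data point will be termed a success; otherwise the data point will be termed a failure". SVR24 is not excepted.

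SAP 3.6.1, which covers Cohort 3 only, also makes unbracketed missing values failures, "except for SVR24, which will be imputed according to SVR12 status". It continues: "Success for SVR12 for subjects who have no further HCV RNA measurements collected will be counted as a success for SVR24". The reason given is that the two endpoints are highly correlated; no figure is offered.

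SAP 6.2.2 applies the 3.6.1 rules to the by-visit response rates and adds: "The 2-sided 95% exact confidence interval based on Clopper-Pearson method will be provided for the proportion". The table list in SAP Appendix 2 has one SVR-by-visit table (15.9.2.2) and one SVR12/SVR24 concordance table (15.9.2.3). The concordance table is restricted to subjects with both values observed.

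**The concern.** The two documents give opposite outcomes for the same subject, and the SAP does not tell the reader so. Its only section on changes from the protocol, 7.8, is confined to safety, and section 6 has no counterpart for efficacy.

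The study tests no hypothesis, so the printed SVR24 rate and interval are the whole result for that endpoint. If any Week 12 responder has no later sample, the rate will exceed the one the protocol defines, and nothing in the table will show how much of it was observed.

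**Working it through.** The documents state no SVR24 rate and no sample-size calculation, so there is no figure of the plan's own to reproduce. The check has three parts.

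**1. Where the rules differ, subject by subject**

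| Week 24 value | Protocol 8.2.2 | SAP 3.6.1 |
|---|---|---|
| Observed | As observed | As observed |
| Missing, success immediately before and after | Success | Success |
| Missing, no later sample, SVR12 failure | Failure | Failure |
| Missing, no later sample, SVR12 success | Failure | Success |

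Only the last row differs, and it differs in one direction. A missing SVR12 that is not bracketed stays a failure in the SAP, so the primary endpoint does not move.

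**2. Size**

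Inputs:
- n = 15, planned for Cohort 3 (SAP 1.2).
- Two-sided 95% Clopper-Pearson interval (SAP 6.2.2).
- s = number of SVR12 successes, and m = number of those with no Week 24 value. Both are assumptions, because the documents give neither. No observed relapse after Week 12 is assumed.

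Formulas:
- SAP rate = s/15. Protocol-rule rate = (s − m)/15. Gap = m/15, which is 6.7 points for each such subject.
- For k successes, the lower limit is the 0.025 quantile of Beta(k, n − k + 1) and the upper limit is the 0.975 quantile of Beta(k + 1, n − k). When k = n, the upper limit is 100% and the lower limit is 0.025^(1/15) = 78.2%.

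| s | SAP rule, any m | Protocol rule, m = 1 | Protocol rule, m = 2 |
|---|---|---|---|
| 15 | 15/15 = 100% (78.2 to 100) | 14/15 = 93.3% (68.1 to 99.8) | 13/15 = 86.7% (59.5 to 98.3) |
| 14 | 14/15 = 93.3% (68.1 to 99.8) | 13/15 = 86.7% (59.5 to 98.3) | 12/15 = 80.0% (51.9 to 95.7) |
| 13 | 13/15 = 86.7% (59.5 to 98.3) | 12/15 = 80.0% (51.9 to 95.7) | 11/15 = 73.3% (44.9 to 92.2) |

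With m = 0 the two columns agree. As a check on the 14/15 limits, the binomial tail at each limit is 0.025.

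**3. Whether a planned output shows the effect**

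- Table 15.9.2.2 uses the SAP rule only.
- The follow-up counts in SAP 4.1 name subjects with no Week 4 sample onward and no Week 12 sample onward. They have no category for Week 12 present and Week 24 absent, which is the imputed group.
- Subtracting the observed SVR24 successes in Table 15.9.2.3 from the SVR24 successes in Table 15.9.2.2 approximates the imputed count. A subject with Week 24 observed but Week 12 missing is absent from the concordance table, so an observed success of that kind would be miscounted as imputed. The HCV RNA listing (16.2.6.1) would resolve such a case.

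**The case against.** The rule is prespecified and reasoned. It stands in the same sentence as the failure rule it modifies. The protocol leaves efficacy details to the SAP (8.4.2), and "The SAP will be finalized before SVR12 analysis database finalization". That answers any suggestion of a data-driven choice. It does not turn the reversal of a rule written in Protocol 8.2.2 into an added detail.

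The SAP also plans a check on its assumption. The concordance table compares SVR12 with SVR24 among observed pairs, and Listing 16.2.6.4 identifies relapses after Week 12. With 15 subjects, the disposition data and the HCV RNA listing would let a careful reader recover the imputed count. This stands: no information is lost. But the reader must rebuild both the count and the protocol-rule interval.

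The amount of missing data is hypothetical. The documents report no Week 12 responder without a Week 24 sample. The Week 24 analysis window runs from day 147 to day 190, which is 21 days before to 22 days after day 168, against a visit window of ±7 days, so moderately early or late samples still count. This stands too: the effect may be zero.

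Finally, neither rule is shown to be nearer the truth. Counting missing as failure can understate SVR24 just as carrying SVR12 forward can overstate it. That is a reason to show both, not a reason to show only the higher.

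**Conclusion.** The concern holds. SAP 3.6.1 reverses the protocol's stated outcome for a Week 12 responder with no later sample, does not identify this as a departure, and plans neither the protocol-rule SVR24 rate with its interval nor a count of imputed successes.

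The effect on the printed rate is zero or upward, at 6.7 points per such subject if 15 are analysed. The consequence is limited to one descriptive secondary endpoint in Cohort 3. SVR12, SVR4 and the virologic-failure criteria do not change. The separate SAP for Cohorts 1 and 2 is not among the documents, so nothing is concluded about them. The point should be fixed, but it does not threaten the primary result.

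**What to change.** In Table 15.9.2.2, print SVR24 with its Clopper-Pearson interval twice, once under Protocol 8.2.2 and once under the SAP 3.6.1 carry-forward, each labelled. Add the number of SVR24 successes imputed from SVR12. In SAP 3.6.1 or section 6, state that the carry-forward departs from Protocol 8.2.2. The SAP rule itself can stay.

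The cost is one sentence, one row and one count in a table already planned, with no new data. The sponsor may have to show a less favourable figure if any Week 12 responder has no later sample.
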